Analysis Plan: We will measure coronary plaque volume using CCTA images at both baseline and 12-months post-treatment initiation. The primary endpoint will be (1) total coronary plaque volume (continuous). Secondary endpoint will be non-calcified coronary plaque volume (continuous). Other outcome measures include (1) calcified plaque volume (continuous), (2) low-attenuation plaque volume (continuous), (3) coronary artery calcification score (continuous), and (4) coronary vessel stenosis (ordinal). The change in endpoint metrics between baseline and 12-month will be estimated for leuprolide versus relugolix versus no ADT. Data transformation to fit statistical assumptions will be done as needed. In addition, we will implement multivariable models that control for potential confounders (e.g. age, statin medication use) using general linear regression and/or logistic regression.

Power: We hypothesized that there will be significantly greater total plaque burden (i.e. summation of total plaque volume of all major coronary territories) increase from baseline to month 12 following GNRHa versus no ADT or relugolix. Using a standard deviation of 30 mm³ for the change in total plaque volume from scans obtained at two time points approximately 12 months apart in the study, 60 participants (30 in each comparative treatment arm) with both baseline and month 12 CCTA would provide 80% power to detect a difference of ≥ 20 mm³ in the change in total plaque volume [$P(X>Y) 0.72$] from baseline to 12 months.

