Aim 2.1: To determine how pre-existing and ADT-augmented inflammatory immune responses impact CV toxicity, we will evaluate pre-treatment, 3-, 6-, and 12-month peripheral blood mononuclear cells (PBMC) samples from all patients enrolled on trial. We will first evaluate the frequency and function of inflammatory immune populations by flow cytometry. While we will include a comprehensive panel evaluating lymphocyte and myeloid populations, we will specifically conduct an in-depth analysis quantifying the frequency, phenotype, and activation of T cells and macrophages. In particular, we will evaluate the frequency of naïve (CD44-CD62L+), effector memory (CD62L^{lo}CCR7-CD27^{lo/int}), central memory (CD62L^{hi} CCR7^{hi} CD44^{hi}), CD4 T-helper subsets (staining for the transcription factors Tbet, EOMES, ROR γ , and GATA), and CD4+ Tregs cells (CD25+GITR+CD127-Foxp3+)⁴⁷. Circulating macrophages will be evaluated for inflammatory M1 (CD80, CD86) and immunosuppressive M2 (CD163, CD206) sub-populations. Immune cells will also be evaluated for expression of GNRH receptors, as well as function by expression of intracellular cytokines associated with T cell activity (including IFNy, TNF α , IL-2, IL-4, IL-6, IL-10, and Granzyme B as we have published^{48,49}) or macrophage activity (Arg1, TNF σ , IL-6, IL-12).

Protocol Title: Mechanism and Predictors of Cardiotoxicity after Prostate Cancer Treatment: A Parallel Cohort and Randomized Trial Comparing Radiation Alone, Radiation plus Leuprolide, and Radiation plus Relugolix

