Analysis Plan: Immune responses (e.g., frequency or function of immune populations) and circulating proteomic biomarkers will first be summarized and plotted by the follow-up time points to illustrate the change pattern over time for all patients and then separated by treatment arms. We will first test whether these biomarker change pattern would be altered by treatment groups (e.g., GNRH-agonist versus GNRH-antagonist) using Kruskal-Wallis test, and then we will link such pattern (e.g., percentage change from baseline for biomarkers) with related CV injury metrics as in Aim 1 using the similar statistical strategy as in Aim 1.2. P-value will be adjusted for multiple testing using Holm-Bonferroni method to control familywise error rate.

Aim 3: To determine how pre-existing genomic alterations promoting inflammatory immunity impact development of CV toxicity following GNRHa versus relugolix, pre-treatment PBMC samples will be subjected to whole exome sequencing to determine alterations to the protein-coding regions of the genome. DNA will be extracted from PBMC and analyzed for quality. Following this analysis, DNA will be fragmented using restriction enzymes and undergo a second round of quality control. Fragmented DNA will be used to generate next-generation sequencing libraries and will undergo capture for exomic DNA sequences (Illumina Nextera Rapid Capture Expanded Exome), followed by amplification and repeated QA/QC. DNA sequencing will be conducted using the Illumina HiSeq platform. The FASTQ data files will be aligned using BWA-MEM, and variants from the human genome will be determined using VarScan and annotated using ANNOVAR. To be considered a valid mutation it will need to comprise at least 2% of the reads, as has been utilized to identify CHIP-related mutations^{27,55}.

Protocol Title: Mechanism and Predictors of Cardiotoxicity after Prostate Cancer Treatment: A Parallel Cohort and Randomized Trial Comparing Radiation Alone, Radiation plus Leuprolide, and Radiation plus Relugolix

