Analysis Plan: The correlation among baseline genomic biomarkers, inflammatory biomarkers, and proteomic biomarkers will be described using Spearman Correlation Coefficient for all patients and by treatment group separately. The association of genomic alterations with CV injury metrics (as defined in Aim 1) will be handled by similar statistical strategy as in Subaim 1.2. Additionally, the association of genetic aberrations with peripheral immune responses (as in Aim 2) will be carried out by similar statistical strategy as in Aim 2.

Other statistical considerations:

Safety Population: All patients receiving at least one dose of GNRHa or Relugolix (for parallel randomized arms) or radiation alone (for parallel single cohort arm) will be considered evaluable for safety analyses.

Intent-to-Treat Population: Patients who are evaluable for safety and who are furthermore evaluable at 12-month CCTA assessment will be considered evaluable for correlative biomarker analyses.

Safety Analysis: All AEs experienced data will be described by summary statistics. Adverse events will be assessed according to CTCAE version 5.0 and will be evaluated by grade, attribution, and organ class. Adverse event listings and tabulated summaries of categorized AEs will be generated for all patients collectively and will be summarized by arms. Vital signs and laboratory data will be summarized for changes over time on study.

Stopping Rule: The two ADT test agents are FDA-approved drugs that are used in clinical practice, and hence no stopping rule for safety is in place officially.

7. Data Specimen Banking

To achieve Aims 2 and 3 discussed above, peripheral blood specimens will be collected longitudinally four times for each enrolled patient (i.e. pre-treatment, 3 months, 6 months, 12 months).

Draw 1 (pre)	Draw 2 (3mo)	Draw 3 (6mo)	Draw 4 (12mo)
Pre-ADT	2-4 months post-ADT initiation	6-8 months post-ADT initiation	12-15 months post-ADT initiation

The blood is collected and processed according to the standard operating practices and regulatory parameters of the Winship biorepository and under the guidance of a board-certified pathologist.

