- Emory Research Management System (ERMS; <https://erms.emory.edu>) Enrollment Fax Cover

The WCSR will enter the subject into the OnCore Research Management System, which is the system of record for Winship Cancer Institute Clinical Trials.

Eligible patients will be enrolled on study centrally at Winship Cancer Institute by the Study Coordinator. When all required test results are available, complete the eligibility checklist and provide the checklist and the supporting documentation to the IRB approved investigator for review and sign-off. Once the

Protocol Title: Mechanism and Predictors of Cardiotoxicity after Prostate Cancer Treatment: A Parallel Cohort and Randomized Trial Comparing Radiation Alone, Radiation plus Leuprolide, and Radiation plus Relugolix

investigator (sub-investigator, Co-Investigator) has signed the eligibility checklist, enrollment may proceed. Oncore and ERMS must be updated to reflect eligibility and on treatment status.

14. Withdrawal of Participants

Participation in the study should continue until one of the following criteria applies:

- Intercurrent illness that prevents delivery of planned radiation therapy or ADT
- Unacceptable treatment-related adverse event(s), including patient death
- Withdrawal of informed consent (subject's decision to withdraw for any reason)
- Noncompliance with treatment plan, including delays to treatment or acquisition of additional diagnostic imaging that significantly exceeds the proposed timeline of study events
- General or specific changes in the patient's condition that render the patient unacceptable to receive further treatment in the judgment of the investigator
- Lost to follow up. In the event of a patient's withdrawal, the Investigator will make every effort to complete the End of Treatment/follow-up procedures specified in the Schedule of Events.

15. Risk to Participants

Radiation therapy +/- hormone therapy (either GNRHa or relugolix) are FDA-approved, guideline-supported standard treatments for prostate cancer. There is no additional risk associated with treatment on study, including the randomized portion of treatment (i.e. GNRHa with Lupron/Trelstar and Relugolix are acceptable ADT options for men with prostate cancer undergoing radiation therapy). There is no additional risk associated with blood draws (which will correspond to blood draws taken at standard clinical intervals to minimize additional appointment or peripheral venous sticks).

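### The population labelled Intent-to-Treat is a dosed, 12-month-CCTA-evaluable set; on the natural reading it governs the randomised biomarker test, and the primary comparison names no analysis set or as-assigned rule

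*Combined protocol and SAP*

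**What the plan says.** Section 6, Other statistical considerations, under the Intent-to-Treat heading: "Patients who are evaluable for safety and who are furthermore evaluable at 12-month CCTA assessment will be considered evaluable for correlative biomarker analyses". The Safety Population just above it supplies the first condition: "All patients receiving at least one dose of GNRHa or Relugolix (for parallel randomized arms"; the parallel cohort enters on radiation alone.

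Section 6, Aim 2.1, describes the blood work differently: "we will evaluate pre-treatment, 3-, 6-, and 12-month peripheral blood mononuclear cells (PBMC) samples from all patients enrolled on trial". Section 7 agrees that "peripheral blood specimens will be collected longitudinally four times for each enrolled patient". The Aim 2 Analysis Plan contains a comparison of the randomised arms: "We will first test whether these biomarker change pattern would be altered by treatment groups (e.g., GNRH-agonist versus GNRH-antagonist) using Kruskal-Wallis test".

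For the primary endpoint, the Aim 1 Analysis Plan says "The change in endpoint metrics between baseline and 12-month will be estimated for leuprolide versus relugolix versus no ADT". It names no population. The only population wording is in the Power paragraph, which counts 30 men per arm "with both baseline and month 12 CCTA".

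Section 14 opens with "Participation in the study should continue until one of the following criteria applies" and lists noncompliance and unacceptable treatment-related events among the criteria. Section 12 expects low dropout but gives no figure.

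**The concern.** Intention-to-treat means that every randomised man counts in the arm to which he was assigned. Here a man must have been dosed and must also have been evaluable by CCTA a year later. Both are post-randomisation facts, and both can depend on treatment. The arms differ in delivery (depot injection against daily tablets with a drug diary) and the trial is open-label, so unequal loss is plausible. If loss differs by arm and is related to the outcome, a comparison among those who remain is biased, in either direction. A report citing an ITT analysis would tell its readers that this had been avoided.

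There is also needless loss of data. A man with 3- and 6-month blood results but no 12-month scan can contribute to a comparison of immune change between arms, yet the definition appears to leave him out.

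For the primary comparison the difficulty is silence. The one set carrying the ITT label is assigned to other analyses, and nothing says in which arm a man who receives the other agent is counted.

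**Working it through.** **1. Which analyses the set reaches.** It is assigned to correlative biomarker analyses. Section 2 describes Aim 2 as the secondary, laboratory-based correlative studies, and the arm-versus-arm Kruskal-Wallis test sits in the Aim 2 Analysis Plan. By data type:

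| Aim 2 analysis | Samples | Effect of requiring a 12-month CCTA |
|---|---|---|
| Flow cytometry, by arm (Aim 2.1) | baseline, 3, 6, 12 months | 3- and 6-month data lost needlessly |
| Plasma cytokines, by arm (Aim 2.1) | same | same |
| Proteomics, by arm (Aim 2.2) | baseline, 12 months | little: last draw and scan fall at about the same time |
| Linking biomarkers to plaque change | any, plus both scans | proper: the scans are needed |

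**2. Size of the selection effect (assumed loss).** From the Power paragraph: SD 30 mm³, difference 20 mm³, 30 per arm. Loss rates and the correlation ρ between loss and outcome are assumptions.

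- Standard error of the difference = 30 × √(2/30) = 7.75 mm³.
- Shift of an arm mean = −ρ × SD × φ(z)/(1 − loss), with z the (1 − loss) normal quantile.
- Loss 10%: φ(1.282)/0.90 = 0.1755/0.90 = 0.195. Loss 3%: φ(1.881)/0.97 = 0.0680/0.97 = 0.070. The gap is 0.125.
- At ρ = 0.8 the shift is 0.8 × 0.125 = 0.10 SD, or 0.8 × 30 × 0.125 = 3.0 mm³, which is 3.0/7.75 = 0.39 SE.

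| Loss, GNRHa v relugolix | ρ = 0 | 0.1 | 0.3 | 0.5 | 0.8 |
|---|---|---|---|---|---|
| 10% v 3% (mm³) | 20.00 | 19.63 | 18.88 | 18.13 | 17.00 |
| 3% v 10% (mm³) | 20.00 | 20.37 | 21.12 | 21.87 | 23.00 |

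Loss of 15% v 5% takes the difference from 20.0 to 16.0 at ρ = 0.8 (0.51 SE). Equal loss gives 20.0 throughout.

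**3. Early biomarker data.** The plan specifies no separate month-3 test, so this only illustrates what the restriction does. With no true effect and loss of 10% v 3% by month 12, keeping only later completers leaves 27 + 29.1 = 56.1 of 60 men on average. In 40,000 simulated trials it shifts the comparison by 0.01 to 0.10 SD (ρ 0.1 to 0.8). Using every month-3 sample gives 0 if all loss comes later, and 0.01 to 0.06 SD if half comes before month 3.

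**4. How far unscanned men could move the primary result.** The plan states no alpha. Its 80% power is approached at one-sided 5% (t test 81.8%, simulated Mann-Whitney 79.8%) but not at two-sided 5% (t test 71.9%), so both are shown.

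Let d be the mean change in unscanned men minus that in scanned men of the same arm, and m the number unscanned. Adjusted difference = 20 + (mG/30)dG − (mR/30)dR, with G for GNRHa and R for relugolix. With opposed departures (dG = −d, dR = +d), significance is lost at d = (20 − critical difference) × 30/(mG + mR).

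| Unscanned | SE (df) | Two-sided 5% | One-sided 5% |
|---|---|---|---|
| 3 v 1 | 8.02 (54) | (20 − 16.09) × 30/4 ≈ 29 mm³ | (20 − 13.43) × 30/4 ≈ 49 mm³ |
| 5 v 5 | 8.49 (48) | (20 − 17.06) × 30/10 ≈ 9 mm³ | (20 − 14.23) × 30/10 ≈ 17 mm³ |

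Bringing the difference to zero takes 20 × 30/4 = 150 mm³ or 20 × 30/10 = 60 mm³. Missing fractions are treated as fixed.

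**The case against.** Four points on the other side have force.

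- **Scope.** The correlative analyses could mean only the step that links biomarkers to plaque metrics, where requiring the scan is right. The wording permits this. Section 2's description of Aim 2 makes the wider reading more natural, but it remains an inference.
- **Agreement between sections.** A reader might infer a flat contradiction between Aim 2.1 (everyone enrolled) and the Intent-to-Treat definition. The documents do not support that: one may say whose samples are assayed and the other who is analysed. The text does not say so, and the two are unreconciled.
- **Effect on the primary result.** A reader might infer that this set governs the primary comparison, or that the plaque result will be materially biased. Neither is supported. The set is not assigned to that comparison, and the Power paragraph already points to men with both scans. The shifts in step 2 apply equally to the wording proposed below; only better retention would reduce them. Section 8 keeps scans blinded until the second is complete, so knowledge of plaque change should not drive loss, though symptoms or events could.
- **Withdrawal.** A reader might infer from Section 14 that men who stop treatment are lost to the 12-month scan. It asks for every effort to complete follow-up procedures listed in a Schedule of Events that is not in the supplied text, so this cannot be judged.

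What stands is the mislabelled set, its likely reach into a randomised test, and the missing primary set and as-assigned rule.

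**Conclusion.** The concern holds as a should-fix matter of definition. In the randomised arms the set labelled Intent-to-Treat is a dosed-completer set. On the natural reading it removes usable 3- and 6-month flow-cytometry and cytokine data from a randomised comparison; proteomics is little affected. The primary comparison has no stated analysis set beyond the Power paragraph's wording, and no rule for analysis by assigned arm.

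The likely numerical effect is modest but unknown in size and direction, because the documents give no loss figure. The limit of about 0.1 SD (0.39 SE) holds for assumed loss of 10% v 3% and ρ up to 0.8; larger or more unequal loss would move it further. The case rests on the definition and the omission, not on a demonstrated large bias.

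**What to change.** - Define ITT as all men randomised to GNRHa or relugolix, analysed as assigned.
- Rename the present set CCTA-evaluable and use it only where both scans are needed.
- Run the randomised biomarker comparison on all randomised men with the relevant samples, with or without a 12-month CCTA. Reconcile Aim 2.1, the Aim 2 Analysis Plan and the population definitions accordingly.
- State that the primary comparison includes every randomised man with both scans, as assigned and regardless of dosing or adherence. Call it an available-data analysis, and report missing scans by arm and reason.

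Two additions are optional good practice. One is a delta sensitivity analysis as in step 4, with alpha and sidedness stated. The other is a Section 14 clarification that men who stop or change ADT are still invited to the planned 12-month CCTA and blood draws, with no change to any rule on stopping treatment.

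The cost is SAP wording and slightly more analysis work. Scans and draws are already planned for every man, and Aim 2.1 already plans to assay everyone enrolled. The Section 14 option would add some follow-up effort.

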At each collection, approximately 20-30 cc of venous blood will be collected in three purple-top tubes with EDTA anticoagulant, and about 6-8 cc of venous blood will be collected in one PAXgene tube. The blood will be procured for mononuclear cells and plasma, and it will be snap-frozen or cryopreserved. Blood samples will be processed via ficoll-hypaque density centrifugation to obtain cellular material.

Winship tissue procurement staff and other authorized personnel will provide the blood samples upon request to investigators on this protocol or their designees. Blood will be distributed according to the prioritization decided by the PIs and study team and utilizing the standard operating procedures of the Winship research biorepository core.

This protocol and a detailed biorepository request will be submitted to the Winship Discovery prostate working groups for review and approval. If approved, deidentified blood and coded, limited datasets will be obtained from the Winship biorepository with oversight from the Winship informatics team under the Emory Honest Broker protocol. Blood will be distributed to [name] Lab according to the standard practices and regulatory parameters of the Winship biorepository, WRISR, and the Winship Cancer Tissue and Pathology Shared Resource (CTPSR). Data will be transmitted through password protected systems within the Emory University/Healthcare Firewall.

8. Sharing of Results with Participants

Each enrolled participant on trial will be eligible to receive results of their coronary CT scans (pretreatment #1, and 12-month #2) after completion of the 12-month study period. All CT scans will be blinded until completion of the 12-month scan (i.e. scan #2). After that period, patients are eligible to

Protocol Title: Mechanism and Predictors of Cardiotoxicity after Prostate Cancer Treatment: A Parallel Cohort and Randomized Trial Comparing Radiation Alone, Radiation plus Leuprolide, and Radiation plus Relugolix

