receive report of the image findings (i.e. scan #1 and #2). These scans are guideline-concordant cardiac screening tests, and findings may be used to appropriately manage patients with regards to his cardiovascular health. As all scans are blinded before completion of #2 scan (i.e. 12 months after enrollment), no scan #1 image findings will be disclosed to patients until after the 12 month study period. Of note, all CT images will be interpreted regarding coronary artery (e.g. stenosis, calcification) and epicardial adipose tissue findings only; any pulmonary, mediastinal, or osseous findings will not be interpreted by the cardiac radiologist.

Blood bank analyses (for Aims 2 and 3) are for research purposes only and will not be disclosed to patients during or after completion of the study period.

9. Study Timelines

Each patient will be enrolled on study for a total of ~12 months, which includes time from pre-treatment coronary CT and blood draw, to 12-month coronary CT and final blood draw. Each patient will undergo XRT +/- ADT for management of localized prostate cancer in the interim.

Based on current volume of newly diagnosed localized prostate cancer eligible for definitive XRT across all Winship Cancer Institute sites, we anticipate to complete accrual of the study (i.e. 3 treatment cohorts, n=30 in each arm; see Figure 5 Study Schema) within 12 months after study opening. Study endpoints for Aim 1-3 (i.e. imaging findings, blood analyses) will be completed on a rolling basis, and thus, we anticipate completion of data acquisition within 24 months after study opening.

Completion of this mixed-methods research will involve a robust multidisciplinary team across Winship, including Radiation Oncology (Drs. [name] and [name]; leading the accrual of patients to trial), Cardiology/Cardiac Imaging (Drs. [name], [name], [name]; leading the coronary CT interpretation on study for Aim 1), Hematology and Medical Oncology ([name]; leading the laboratory analyses of peripheral blood for Aims 2-3), and Biostatistics ([name]; leading all statistical analyses for Aims 1-3).

Projected funding start date: 12/1/2021

Projected funding end date: 11/30/2023

Timeline for Completion of Proposed Research	Months	3	6	9	12	15	18	21	24
Aim 1. Effect of leuprolide versus relugolix on coronary plaque development using non-invasive cardiac imaging									

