Subaim 1.1. Relationship between ADT and accelerated coronary plaque development/rupture									
Subaim 1.2. How baseline cardiac imaging biomarkers correlate with ADT-associated plaque development									
Aim 2. Relationship between leuprolide versus relugolix on immune effector responses implicated in atherosclerosis									
Subaim 2.1. How pre-existing and ADT-augmented inflammatory immune responses impact CV toxicity									
Subaim 2.2. How circulating proteomic biomarkers predict for cardiac toxicity									
Aim 3. How pre-existing genomic alterations impact development of cardiac toxicity following leuprolide versus relugolix									
Subaim 3.1: Identification of how pre-existing genomic alterations impact immune responses and CV toxicity									

10. Inclusion and Exclusion Criteria

Inclusion:

- Men ≥18 years old
- Non-metastatic prostate cancer
- Non-metastatic, biochemically recurrent prostate cancer
- Plan to undergo curative-intent pelvic radiation therapy (photons or protons) with or without brachytherapy

Exclusion:

- Metastatic prostate cancer requiring >24 months of ADT
- Prior invasive cancer diagnosis
- Prior exposure to androgen deprivation therapy
- Prior exposure to chemotherapy, immunotherapy, or radiation therapy

Protocol Title: Mechanism and Predictors of Cardiotoxicity after Prostate Cancer Treatment: A Parallel Cohort and Randomized Trial Comparing Radiation Alone, Radiation plus Leuprolide, and Radiation plus Relugolix

- History of cardiac bypass surgery, percutaneous coronary intervention, or cardiac device implantation
- Renal insufficiency, contrast allergy, or arrhythmias that limits feasibility of CT acquisition

11. Vulnerable Populations

Not applicable. This study does not involve individuals who are vulnerable to coercion or undue influence, such as pregnant women, children/minors, cognitively-impaired, prisoners, etc.

12. Local Number of Participants

Our accrual goal for this protocol is 90 patients (n=30 in each arm).

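### Section 8 withholds scan 1 findings from patients for about 12 months and, in the supplied protocol text, states no exception for a critical coronary finding

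*Combined protocol and SAP*

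**What the plan says.** Section 8 (Sharing of Results with Participants) sets the rule twice. First: "All CT scans will be blinded until completion of the 12-month scan (i.e. scan #2". Then, for patients: "no scan #1 image findings will be disclosed to patients until after the 12 month study period". The first statement does not say who is blinded; the second names patients only.

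The same section treats the scans as clinically useful: "These scans are guideline-concordant cardiac screening tests, and findings may be used to appropriately manage patients with regards to his cardiovascular health". It also says that "all CT images will be interpreted regarding coronary artery (e.g. stenosis, calcification) and epicardial adipose tissue findings only". Section 9 gives the cardiology and cardiac imaging investigators the task of "leading the coronary CT interpretation on study for Aim 1".

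Section 10 excludes men with "History of cardiac bypass surgery, percutaneous coronary intervention, or cardiac device implantation". It does not exclude a man whose first severe lesion is found on scan 1.

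**The concern.** A coronary CT can show a severe lesion in a man without symptoms. Section 8 presents the result as something that can guide his care, then bars telling him for about a year. During that year two of the three groups receive hormone therapy, and the trial exists because one form of it is suspected of accelerating coronary disease. Section 16 itself suggests that high-risk men may gain from cardiac optimisation before treatment.

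Masking scan 1 has a sound purpose: it limits changes in cardiac care that would blur the 12-month plaque comparison. The question is whether the rule needs to be absolute, and what a narrow exception would cost the primary analysis.

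**Working it through.** **Is there an exception anywhere in the supplied text?** No formula applies here; the sections are set side by side.

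| Place | What it covers | Route for a critical scan 1 result? |
|---|---|---|
| Section 8 | Blinding and release of CT results | None stated |
| Sections 5 and 6 | Scan acquisition, plaque analysis, endpoints | None stated |
| Section 14 | Withdrawal | None stated |
| Section 15 | Risks of treatment, blood draws and CT radiation | None stated |
| Section 19, adverse events | Recording, grading, reporting, treatment of events | None stated; a silent lesion already present at baseline is not clearly an event that starts or worsens after consent |
| Section 19, monitoring | Weekly investigator meeting on study data; data safety committee oversight | General; CT findings not named, and the meeting may itself fall under the blinding |
| Section 22 | Consent process | None stated |

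**What would a narrow exception cost the primary comparison?** Inputs from the Power paragraph of Section 6: SD of change 30 mm³, target difference 20 mm³, 30 men per arm. Assumption, not from the documents: each released man's change in plaque volume moves by 1 SD (30 mm³) because his treatment changes.

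1. *Shift in one arm mean.* k × 30/30 = k mm³. One man gives 1.0 mm³ (1/20 = 5% of the target difference); two give 2.0 mm³ (10%).

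2. *Net shift between randomised arms if release is decided before randomisation.* Let K of 60 men be released, with a of them falling in one arm. The net shift is (2a − K) mm³. Its mean is 0 and its SD is 2 × √[K × 0.25 × (60 − K)/59], ignoring strata. For K = 1, 2, 3 the SD is 1.00, 1.40 and 1.70 mm³. For K = 2, the chance that both men fall in one arm is 2 × C(30,2)/C(60,2) = 870/1770 = 0.492.

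3. *Power with released men kept in.* If k men per arm move by 30 mm³, then with p = k/30 the SD becomes √[900 + 900·p(1 − p)]. Power is from a two-sample t-test with 58 degrees of freedom and noncentrality 20/(SD × √(2/30)), alpha 0.05.

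| k per arm | SD (mm³) | Two-sided power | One-sided power |
|---|---|---|---|
| 0 | 30.00 | 0.719 | 0.818 |
| 1 | 30.48 | 0.705 | 0.807 |
| 2 | 30.92 | 0.693 | 0.797 |

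The k = 0 row is the comparison point for the plan's 80%. The plan states neither the test nor its sidedness, so both are shown. The loss is about 1.1 to 1.4 percentage points for one man per arm and about 2.1 to 2.6 for two.

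These figures measure the price of the exception; they have no bearing on whether the gap exists. They also do not cover a man who is stented or bypassed between scans, because his two plaque volumes may not be comparable at all.

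**The case against.** The strongest reply has four parts.

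*There is a safety forum.* Section 19 has the principal investigator, investigators and coordinators meet weekly to review study data for subject safety, and a data safety committee looks at safety and risk-benefit. Section 22 makes the consenting treating physician a co-investigator. A meeting of that kind could catch a severe lesion. This stands as a reason not to say the trial has no safety oversight. It does not close the gap: no text says CT results go to that meeting, or that the meeting may override Section 8.

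*Nobody may be sitting on a known lesion.* A reader might infer that investigators will know of a critical lesion and conceal it. The documents do not support that. They do not say who is blinded, they bar disclosure only to patients, and they give no date for reading scan 1. Section 9 says endpoint work is done on a rolling basis, which does not promise a prompt read. If scans are read in pairs after month 12, the gap is the lack of an early read rather than the withholding of a known result. The fix covers both.

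*The choice is open and consented.* The masking is stated plainly, and the consent form or Schedule of Events may contain a release rule. Neither was available, so the claim is limited to the supplied protocol text. A rule stated without qualification in Section 8 should still carry its own exception.

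*Ordinary care continues.* A reader might also infer that a man with a cardiac event would go untreated. That does not follow: Section 19 requires adverse events to be treated appropriately, and nothing restricts usual cardiac care. The gap concerns the man without symptoms.

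**Conclusion.** The point holds for the supplied protocol text and should be fixed. Section 8 has no stated route for releasing a critical coronary finding from scan 1, and no other supplied section provides one. The rule covers all 90 men for about 12 months. The number who would have a critical lesion cannot be given: the documents report no prevalence, and it could be zero. How the gap would play out depends on two things the protocol leaves open, namely who is blinded and when scan 1 is read.

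A narrow exception costs little precision under the 1 SD assumption. If it is applied before randomisation, it adds no expected bias between the two randomised arms. That protection does not extend to comparisons with the non-randomised radiation-alone cohort.

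Release when scan 2 is never done is a minor wording matter. A reader might infer that such a man never gets his result, since unblinding is tied to scan 2. But Section 8 also makes each enrolled participant eligible "after completion of the 12-month study period" and equates scan 2 with 12 months after enrolment, so release at month 12 is the more natural reading.

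**What to change.** Keep the default masking and amend Section 8 as follows.

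- **Say who is blinded**: patients, treating physicians, image readers, or some of these.
- **Add a narrow critical-findings exception.** The cardiology investigators and IRB set an anatomical threshold in advance. The existing cardiac imaging team reads scan 1 promptly against it, without knowledge of arm, and releases a critical result to the treating physician and the patient.
- **Place that read before randomisation where possible.** Section 6 calls scan 1 only pre-treatment, and Section 22 lists randomisation straight after enrolment, so the order should be stated. A release triggered by a later cardiac event is not proposed, because that trigger comes after randomisation and could differ by arm.
- **Log** each release and any change in cardiac treatment that follows. Statin use is already a named confounder in Section 6. The log matters most for the radiation-alone comparison.
- **Keep released men in the primary analysis** where scan 2 plaque volume is measurable. State in advance how men revascularised between scans are handled, for example by excluding treated segments from both scans, with a sensitivity analysis. Section 6 already assesses plaque by segment.
- **Minor wording**: say that scan 1 is released at month 12 or at withdrawal if scan 2 is never done. Section 14 says that "the Investigator will make every effort to complete the End of Treatment/follow-up procedures specified in the Schedule of Events", but not what happens to scan 1 if that effort fails.

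The cost is a protocol and consent amendment, a prompt baseline read if that is not current practice, and a few men whose treatment may change before scan 2, with the small power loss shown above. Plaque volume comes from an external analysis service (Section 6), so a separate safety read need not alter the endpoint measurement.
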